9.4 Evaluations and Endpoints – Second Line Analysis

9.4.1 Nonparametric Analysis

9.4.1.1 Operationalizations in Final Protocol

As a sensitivity analysis to the primary parametric approach, a nonparametric analysis will be performed for the two primary hypotheses.

The nonparametric procedures will be performed by means of the Wilcoxon-Mann-Whitney test. The Wilcoxon-Mann-Whitney test (WMW test) is the well-known robust test attributed to Wilcoxon (Wilcoxon 1945) and Mann and Whitney (Mann et al. 1947); for details of the test see e. g. Armitage, Berry, and Matthews (Armitage et al. 2002), or Sprent and Smeeton (Sprent et al. 2001).

The Mann-Whitney estimator (MW) is the associated effect size measure for the Wilcoxon-Mann-Whitney test (WMW test). It is a robust but highly sensitive effect size measure to determine the magnitude and direction of the treatment effects. It is recommended by many authors for its sensitivity and robustness in all data situations (Agresti et al. 1984, Brunner et al. 2000, Munzel et al. 2003, D'Agostino et al. 2006, Brunner et al. 2013, Kieser et al. 2013) for ordinal scales in non-inferiority trials it is even regarded as the 'gold standard' see, e.g. Design and Analysis of Non-Inferiority Trials (Rothmanns et al. 2011). Technically, the MW gives the probability that a randomly chosen subject of the test group is better off than a randomly chosen subject of the comparison group (with the probability ranging from 0 to 1, with 0.5 indicating equality); it is statistically defined as: P (X<Y) + 0.5 P (X=Y).

The relevant benchmarks for the Mann-Whitney effect size measure (MW) are as follows (Colditz et al. 1988):

0.29	large inferiority
0.36	medium sized inferiority
0.44	small inferiority
0.50	equality
0.56	small superiority
0.64	medium sized superiority
0.71	large superiority

Under the assumption of a normal distribution the defined non-inferiority margin AUC 25 mm x days with common standard deviation 75 mm x days, (see [protocol] section 11.4) can be re-expressed in terms of the Mann-Whitney statistic: the raw scale margin results in a standardized mean difference of 25/75 = 0.33, which can be directly transformed to a Mann-Whitney margin of 0.407 (Rahlfs et al. 2014). This margin is consistent with the nonparametric NI bound of 0.40 in a previous NI trial (Gonzalez et al. 2013).

In addition, a non-parametric repeated measurement analysis will be performed by means of the generalized Wilcoxon-Mann-Whitney test (Wei-Lachin procedure), combining the repeated observations by a simultaneous, directional test.

9.4.1.2 Additional Operationalizations

- The nonparametric procedures will be performed for the FAS and PP analysis set as sensitivity analyses for the primary parametric approach. The univariate analysis will be performed by means of the Wilcoxon-Mann-Whitney (WMW) test for the area under the curve (AUC) of pain on passive movement in Visual Analog Scale (VAS) from baseline to Day 4. The repeated measurement analyses will combine the repeated observations of pain on passive movement (VAS) at Day 2, 4, 7 and Final Visit by means of the generalised Wilcoxon-Mann-Whitney test (Wei-Lachin procedure, directional test).
- Descriptive Procedures: TESTIMATE V6.5.14; PROC BASIC STATISTICS / SCIENCEGRAPH V4.9.39
- Test Procedures: TESTIMATE V6.5.14; PROC WILCOXON-MANN-WHITNEY-U-TEST / SCIENCEGRAPH V4.9.39 / PROC MULTIVARIATE COMPARISONS -WEI-LACHIN – DIRECTIONAL

9.4.2 Stratification

9.4.2.1 Operationalizations in Final Protocol

In order to control for center effects, a robust stratified analysis will be performed for the primary efficacy criterion applying the Cochran-Mantel-Haenszel procedure with adjustment for centers (CMH pooling, also known as van Elteren pooling). This procedure is robust also with very low sample sizes per center and group.

In order to control for effects of delayed "Day 4" assessments (Day 4+1), a robust stratified analysis (CMH) will be performed for patients with and without delay.

In order to ensure the data integrity of the trial and to exclude potential bias introduced by partial unblinding, a separate analysis of problematic and non-problematic cases will be conducted with subsequent meta-analytic pooling and test for overall effect and heterogeneity.

Further details will be defined in an update of the Statistical Analysis Plan (SAP). (revised per Amendment to protocol version 3.0)

9.4.2.2 Additional Operationalizations

- The robust stratified analyses will be performed for the FAS and PP analysis set as sensitivity analyses for the primary parametric approach by means of the Cochran-Mantel-Haenszel (CMH) pooling procedure with Wilcoxon scores (Peto-Wilcoxon test).
 - Adjustment for centers by means of the CMH pooling procedure will be performed for the area under the curve (AUC) of pain on passive movement in Visual Analog Scale (VAS) from baseline to Day 4 with centers as strata. Small centers will technically be pooled. According to protocol, the final pooling benchmark is to be decided at the time of the blind review of the soft lock data with documentation in the final Statistical Analysis Plan (see ICH Guidance E9 §3.2 "any case decisions concerning this approach should always be taken blind to treatment, for example at the time of the blind review"). Based on the softlock data, the pooling benchmark for small centers is set to N<20 (virtual center labelled as "center 99"). This way, the sensitivity analysis will be based on 12 center strata and one virtual center, which is regarded as reasonable procedural size for the sensitivity analysis.

 - Adjustment for patients with and without delayed "Day 4" assessments (Day 4+1) will be performed for the area under the curve (AUC) of pain on passive movement in Visual Analog Scale (VAS) from baseline to Day 4.
- Due to serious risk of bias, the "problematic" cases will be evaluated separately and will not be part of the confirmatory or secondary analyses (for details, see section 8 Changes to the Protocol).
- Test Procedures: TESTIMATE V6.5.14; PROC PETO-WILCOXON-TEST.

9.5 Accounting for Missing Data

9.5.1.1 Operationalizations in Final Protocol

The pre-planned analysis procedures are as follows:

1. Last Observation Carried Forward [LOCF] (Applied to all Efficacy Analyses)

A LOCF analysis (Last Observation Carried Forward) will be performed as first line analysis. LOCF will be applied for missing values regardless of the reason for discontinuation.

2. Last Percentile Carried Forward [LPCF] (Applied as Sensitivity Analysis to the First Line Efficacy Analyses)

The LPCF method carries forward the change information, using the percentile value with back transformation to raw scale, instead of last value carried forward. This approach was recently developed and recommended by O'Brien, Zhang and Bailey in 2005 (O'Brien et al. 2005). The results of this method are well comparable to the mixed-effect models for repeated measures (MMRM), without making the corresponding parametric assumptions. According to their simulation study the calculated estimators should be negligibly biased by missing data.

Additional sensitivity analyses resulting from the blind review of the data and further technical details will be provided in this final Statistical Analysis Plan.

The frequency and type of missing values will be documented in the Clinical Trial Report.

9.5.1.2 Additional Operationalizations

- The imputation by means of Last Observation Carried Forward [LOCF] will be applied to all first line analyses (confirmatory and exploratory) with the exception of the secondary efficacy variables no. 7 and 8 (see section 9.3.2). Imputation of missing values is performed using the last existing follow-up value. The imputation by means of Last Percentile Carried Forward [LPCF] will be omitted due to the marginal number of missing efficacy values.
- The number of non-missing values will be documented in the Clinical Trial Report for all variables and evaluations (valid number). The frequency and type of missing values will be documented in the Clinical Trial Report for the primary efficacy variable (area under the curve, AUC) of pain on passive movement in Visual Analog Scale (VAS) from baseline to Day 4.
- The standard ensemble of classic and robust summarizing statistics (see section 9.1) will be provided for the pre-specified imputation as well as for *data as available*, i.e. without imputation.

9.6 Evaluations and Endpoints – Safety

9.6.1.1 Operationalizations in Final Protocol

Safety variables are:

- AEs
- other observations related to safety (physical examinations, vital signs).

All safety summaries will be performed on the Safety Analysis Set if not indicated otherwise. For vital signs, no formal testing will be applied to detect imbalances between the treatment groups.

AEs will be presented by MedDRA Preferred Term and System Organ Class in different categories.

Incidence rates of AEs, SAEs and AEs related to investigational product will be reported. The duration of exposure to IMP and the amount of IMP used for the three treatment groups (Traumed® gel, diclofenac gel and placebo gel) will be analyzed.

9.6.1.2 Additional Operationalizations

Descriptive procedures will be performed according to section 9.1.

9.7 Analysis Populations

9.7.1.1 Operationalizations in Final Protocol

Safety Analysis Set: Randomized patients who receive at least one dose of investigational medication will form the Safety Analysis Set. The Safety Analysis Set will be used for all analyses of safety, tolerability, and background characteristics. For this set, the exposure to IMP will be also analysed.

Full Analysis Set (FAS): The Full Analysis Set is a subset of the Safety Analysis Set consisting of all patients with acute unilateral Grade 1 or Grade 2 sprain of the lateral ankle, for whom both baseline and Day 4 VAS values of pain are available. The Full Analysis Set will be used for the Intent-to-Treat (ITT) analysis.

Per-Protocol (PP) Set: Patients in the Full Analysis Set without major protocol deviations will form the PP Set. The PP Set will be used for the per-protocol analysis of the efficacy parameters. The same efficacy evaluations as in the FAS are planned. Relevant differences between the FAS and PPS will be evaluated in the Clinical Trial Report.

Protocol deviations will be collected during the entire trial and will be classified as minor or major at the Blind Data Review Meeting (BDRM). Protocol deviations that may affect the efficacy outcome of participants will be classified as major. The decision about major protocol deviations and assignments to populations will be documented in the BDRM minutes.

9.7.1.2 Additional Operationalizations

- In order to preserve validity and integrity of the trial, all confirmatory and secondary analyses will be based on the group of non-issue patients (for details see section 8 Changes to the Protocol). As stated in the 'Amendment Summary Document for Substantial Protocol Changes', the sample size was proactively enhanced to ensure planned power and validity for evaluating the pre-defined trial objectives also in case that only non-compromised cases allow valid and unbiased conclusions. Results of issue patients will be provided separately in the Appendix of the Clinical Trial Report (CTR).
- FAS: VAS availability at Day 4 is referring to LOCF (primary analysis).
- PP: premature discontinuations due to "lack of efficacy", "adverse event", or
 "lack of efficacy" and "adverse event" (i.e. drug-related premature
 discontinuations) will not be excluded from the PP analysis, regardless of any
 existing protocol deviation. Benchmarks for "Major Protocol Deviation" (final
 BDRM decisions):
 - Grade 3 determination after Visit 3
 - VASPM V1 < 50
 - Missing VASPM at V1 or V3 (Related to ,Data as Available')
 - Visit 2 \leftrightarrow Day 2 (Protocol Day 2)
 - Visit 3 < Day 4 or > Day 5 (Protocol Day 4 + 1 Day)
 - Visit $4 < \text{Day } 6 \text{ or } > \text{Day } 9 \text{ (Protocol Day } 7 \pm 1 \text{ day)}$
 - Compliance < 80% at V3 or V4
 - Premature Discontinuation (not drug-related)
 - The analysis populations (Safety, FAS, and PP) are listed individually in the Appendix of the final Statistical Analysis Plan.

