5.3.1. Inclusion Criteria

Potential study patients must meet the following inclusion criteria:

1. Acute unilateral Grade 1 or Grade 2 sprain of the lateral ankle
2. ≥ 18 years of age
3. Legally competent male or female outpatient

-
4. Injury occurred within previous 24 hours before first treatment expected
 5. Signed Informed Consent
 6. After 5 minutes of rest, pain on passive movement by investigator measured by Visual Analog Scale (VAS) >50 mm
 7. Not pregnant (as proven by negative pregnancy test in case of woman of childbearing potential before first study drug administration) or breast-feeding. Females of childbearing potential must agree to maintain highly effective birth control throughout the study (see all details in section 9.6). Such methods include:
 - oral, intravaginal, transdermal combined (oestrogen and progestogen containing) hormonal contraception associated with inhibition of ovulation,
 - oral, injectable, implantable hormonal contraception associated with inhibition of ovulation, intrauterine device (IUD), intrauterine hormone-releasing system (IUS), bilateral tubal occlusion, vasectomized partner (if received medical assessment of the surgical success), sexual abstinence (only if defined as refraining from heterosexual intercourse during the entire period of trial participation).

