5.3.2. Exclusion Criteria

Potential study patients will be excluded if at least one of the following exclusion criteria is present:

1. Similar injury affecting the same joint within the past 6 months
2. Bilateral ankle injury
3. Grade 3 ankle sprain
4. Fracture of the ankle (It should be excluded by using e.g. the Ottawa Ankle Rules. In case of any doubt the exclusion of fracture by x-ray should be considered as per standard of care)
5. Chronic joint disorders such as clinically relevant osteoarthritis or aseptic arthritis
6. Disorders that may lead to joint oedema for other reasons than ankle sprain (such as heart failure, thrombosis, lymphedema and others)
7. Diagnosis requiring bed rest, hospitalization, surgery, or use of any cast during the planned treatment period
8. Debilitating acute or chronic illness
9. Use of systemic and /or topical corticosteroids in the previous 8 weeks, any analgesics (e.g. paracetamol/ acetaminophen) in the previous 24 hours before

Screening Visit, or 48 hours in the case of long-acting NSAID, cyclooxygenase type 2 (COX-2) specific inhibitors, or tramadol and other opioids. Low dose acetylsalicylic acid (70 – 100 mg per day) for anti-thrombotic therapy is permitted if doses are stable for the month prior to Screening Visit and planned to be stable during the entire study

10. History of sensitivity to any component of the study drugs (including e.g. paracetamol/ acetaminophen intolerance; patients in whom asthma attacks, skin rash or acute rhinitis are triggered by acetylsalicylic acid or non-steroidal anti-inflammatory drugs (NSAIDs)
11. Unwilling or unable to comply with all the requirements of the study protocol
12. Concurrent injury to proximal structures in ipsilateral lower extremity (i.e. concurrent shin, knee, thigh, or hip injury)
13. History of ligament avulsion, fracture or surgery to the affected lower extremity
14. Presence of infections and/or skin diseases in the area of the study treatment site (including psoriasis)
15. Any previous treatments of the injured ankle, whether topical or systematic, are prohibited except RICE (simultaneous combination of all 4 elements Rest, Ice, Compression and Elevation, which is restricted to be used until starting treatment with the investigational drug)
16. Participation in any clinical study within the past 4 weeks
17. Any relationship of dependence with the sponsor or with the investigator.

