7.2. Description of Patient Visits

7.2.1. Screening / Baseline Visit (Day 1)

Day 0 is defined as the day of injury. The day of inclusion to the study is Day 1. If the patient is included into the study on the same day when the injury has occurred, Day 0 and Day 1 are identical. The date and time of injury and date and time of the first treatment with investigational drug has to be documented in the eCRF to ensure that the time difference between both events does not exceed 24 hours.

Suitable outpatients will be asked by the investigator about their willingness to be included in the clinical trial. The patient is to be informed verbally and in writing in the appropriate language about the nature and purpose of the study, the treatments to be administered, the possible risks and discomfort, the benefits to be expected, and how data collected in this trial will be handled and shared. The patient informed consent form is to be signed and dated by the patient and countersigned by the investigator prior to proceeding with the Screening/ Baseline Visit procedures. The investigator will provide each patient with a second original of the signed and dated informed consent form. See section 1.3 for more details.

Patients who have signed the patient informed consent form will be assessed if they meet all inclusion but none of the exclusion criteria.

Only patients who fulfil all entry criteria will be enrolled and will receive a unique 7-digit patient number (in former protocol versions referred to as 'E-code').

The following study procedures are to be performed:

- Check of inclusion/ exclusion criteria
- Record medical history and demographics
- Review and record previous/ concomitant treatments for the sprained ankle including use of RICE (i.e., the simultaneous combination of all 4 elements rest, ice, compression and elevation) or of parts of these 4 measures
- Review and record previous/concomitant treatments for any other clinical condition(s) also with respect to disallowed medication
- Ankle sprain-related measurements:
 - FAAM-ADL

-
- VAS for evaluating pain at rest for baseline. VAS for pain on passive movement by investigator for inclusion and for baseline. Date and time of assessment will be recorded. Each pain assessments should take place at the same time (+/- 1 hour related to baseline assessment time) at each visit whenever possible

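### Beyond sprain grade and laterality, the per-protocol set enforces only one entry criterion, at a looser limit than the protocol, and waives it for patients who stop for lack of efficacy or an adverse event

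*SAP*

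**What the plan says.** Protocol 11.1.3 and SAP 9.3.1.1 base the confirmatory non-inferiority comparison with diclofenac gel on the PP set. SAP 9.7.1.1 defines PP as the Full Analysis Set (FAS) patients without major deviations, and gives a general rule: "Protocol deviations that may affect the efficacy outcome of participants will be classified as major".

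SAP 9.7.1.2 then sets out the benchmarks for a major deviation as final decisions of the Blind Data Review Meeting (BDRM). They are: Grade 3 found after Visit 3; baseline pain on passive movement below 50 mm; missing pain on passive movement at Visit 1 or Visit 3; Visit 2 not on Day 2; Visit 3 outside Days 4 to 5; Visit 4 before Day 6 or after Day 9; compliance below 80%; and premature discontinuation that is not drug-related.

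The same section says that patients who stop for lack of efficacy, an adverse event or both "will not be excluded from the PP analysis, regardless of any" existing deviation.

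On entry, Protocol 5.3.1 requires pain on passive movement "measured by Visual Analog Scale (VAS) >50 mm" and "Injury occurred within previous 24 hours before first treatment expected". Protocol 7.2.1 has the times of injury and first treatment recorded in the eCRF to ensure that the "time difference between both events does not exceed 24 hours". Protocol 5.3.2 excludes, among others, "Similar injury affecting the same joint within the past 6 months" (exclusion 1), recent corticosteroids or analgesics (exclusion 9) and earlier treatment of the injured ankle other than RICE (exclusion 15).

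**The concern.** A non-inferiority analysis is usually run on PP because patients outside the target population, or not treated as planned, tend to shrink the difference between arms, and a smaller difference makes non-inferiority easier to claim. The protocol itself chooses PP here as the more conservative set. That holds only if the PP rules remove such patients, and remove them for reasons that do not depend on how they did on treatment.

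Two features of SAP 9.7.1.2 work against this. Several entry criteria that bear on early pain have no benchmark. And the waiver covers every deviation, including those present before the first dose. Keeping treatment failures in PP is sound. Keeping a patient who was never eligible, only because that patient later stopped for lack of efficacy, makes membership depend on a post-randomisation event that treatment can influence.

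**Working it through.** **Limits side by side**

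| Item | Protocol | SAP 9.7.1.2 benchmark | Gap |
|---|---|---|---|
| Grade 1 or 2, unilateral, lateral | inclusion 1, exclusions 2 and 3 | through the FAS definition, plus Grade 3 found after Visit 3 | none of note |
| Baseline pain on passive movement | above 50 mm | major if below 50 mm | exactly 50 mm is ineligible yet per-protocol |
| Injury to first dose | at most 24 hours, timed in the eCRF | none | untested |
| Exclusions 1, 9 and 15 | excluded | none | untested |
| Visit 4 | Day 7 ± 1, so up to Day 8 | major if after Day 9; the line cites Day 7 ± 1 | Day 9 is out of window yet per-protocol |

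The Visit 4 gap matters because SAP 9.3.1.2 adds the AUC to Day 7 to the confirmatory sequence (hypotheses 3 and 4). AUCs use actual measurement times. Counted from Day 1, a Day 9 visit closes an interval of 8 days, against 6 for Day 7 and 7 for the last day in window.

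**The waiver.** Take two patients with a baseline of 30 mm. One completes: 30 < 50, a major deviation, so out of PP. The other stops for lack of efficacy: same deviation, but waived, so in PP. The waiver does not lift the FAS conditions, so grade and laterality still apply to the second patient.

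**Size, as an illustration**

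Plan's own figure first (Protocol 11.4: difference 25, SD 75, 291 vs 146, two-sided 0.05):
- SE = 75 × √(1/291 + 1/146) = 7.61
- Power = Φ(25/7.61 − 1.96) = 90.8%, which agrees with the stated 90% or more.

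Non-inferiority test, with assumed PP numbers of 312 vs 156. These are the pre-enlargement arm sizes; 808 − 184 issue patients = 624 gives the same total. The actual PP counts are not known here.
- SE = 75 × √(1/312 + 1/156) = 7.354
- Let the true difference in eligible patients equal the margin, 25, and let a share f of PP be undetected violators who keep a share k of that difference. The mean difference is then 25 × (1 − f(1 − k)).
- One-sided error = Φ(25 f(1 − k)/7.354 − 1.96)

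| f | k = 0 (no difference in violators) | k = 0.5 |
|---|---|---|
| 0 | 2.5% | 2.5% |
| 2% | 2.9% | 2.7% |
| 5% | 3.7% | 3.0% |
| 10% | 5.3% | 3.7% |

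Example: f = 10%, k = 0 gives Φ(2.5/7.354 − 1.96) = Φ(−1.62) = 5.3%. Neither f nor k is given in the documents.

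**The case against.** A reader might infer that PP does not enforce the entry criteria at all apart from baseline pain. The documents do not support that. PP sits inside the FAS, which is limited to acute unilateral Grade 1 or 2 lateral sprains. Grade 3 found after Visit 3 is a benchmark. Protocol 5.3.4 lists randomisation in error despite failed entry criteria as a reason for withdrawal, and a patient so withdrawn leaves PP as a discontinuation that is not drug-related.

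A reader might also infer that entry violators are present in PP, and that the low major-deviation rate in non-issue patients (1.9% in SAP section 8; 0.019 × 624 ≈ 12 patients) shows the list to be too narrow. Neither follows. The 1.9% counts detected deviations and fits good conduct equally well. The benchmarks were set on blinded data, and a missing criterion may mean only that no violation was seen. The per-patient assignments (SAP 13.2) and the BDRM minutes were not available to this review.

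The general rule in SAP 9.7.1.1 also remains in force, and SAP section 7 codes deviations from the definitions in the final SAP, which can be read to include it. This is the strongest defence. It shows that the 24-hour limit may have been applied, but not that it was: 9.7.1.2 presents the list as the final benchmarks and does not mention it. And the general rule cannot rescue the waiver, which overrides any deviation however classified.

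It is fair that the 50 mm gap concerns a single value, that Visit 4 pain does not enter the Day 4 AUC, and that the waiver matters only for patients who both failed entry and stopped for a drug-related reason. No direction of bias is shown for that overlap.

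**Conclusion.** The point holds in limited form. Three things can be read directly from the text: the waiver makes PP membership among baseline entry failures depend on outcome; two limits are looser than the protocol (exactly 50 mm, and Day 9); and the 24-hour limit, timed in the eCRF for this check, has no benchmark, nor do exclusions 1, 9 and 15, although SAP 9.7.1.1 makes deviations that may affect efficacy major.

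The size is unknown. The range from 2.9% (f = 2%) to 5.3% (f = 10%) is a worst case that assumes no treatment difference in violators, a true difference at the margin, SD 75 and 312 vs 156 patients. If violators keep half the difference, it is 2.7% to 3.7%. These figures show the direction and the order of magnitude; they are not an estimate of actual error inflation. The case for change rests on a clean definition of a confirmatory analysis set.

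**What to change.** In SAP 9.7.1.2, before unblinding:

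1. Limit the waiver to deviations that the discontinuation itself causes (missing Visit 3, visit windows, compliance, premature discontinuation). Baseline entry failures are then excluded whatever the outcome, and treatment failures among eligible patients stay in PP.
2. Set the PP limits to baseline pain on passive movement of 50 mm or less and Visit 4 after Day 8, or justify the wider limits.
3. Add as major deviations a first dose more than 24 hours after injury, and those entry violations that may affect efficacy, for example exclusions 1, 9 and 15. Listing all of exclusions 1 to 15 would go too far: some, such as a history of sensitivity (10), need not affect efficacy, which is the test in SAP 9.7.1.1.

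The cost is SAP wording and blinded re-coding. Time and grading of injury, entry criteria and VAS are already eCRF domains (SAP 13.4.2, Table 3), and SAP section 3 places finalisation after hard lock but before unblinding approval. PP may lose a few patients. The planned sample size does not change.
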